3. STUDY OBJECTIVES AND PURPOSE

3.1. Primary objective

The primary objective is to demonstrate the superiority of bumetanide (0.5mg BID) oral liquid formulation compared to placebo in the improvement of ASD core symptoms after 6 months of treatment in ASD children aged from 2 to less than 7 years old.

3.2. Secondary objectives

- To assess the effect of bumetanide on the other efficacy endpoints
- To assess the safety of bumetanide
- To confirm the acceptability and palatability of the oral liquid formulation
- To describe the bumetanide effects on patients quality of life
- To improve existing pharmacokinetic model of bumetanide in this population.

3.3. Exploratory objectives

To describe the Bumetanide effect on utility index scores

4. STUDY DESIGN

4.1. Endpoint(s)

Table (4.1) 1 - Endpoints

	Objectives	Endpoints
Primary	To demonstrate the superiority of bumetanide (0.5mg BID) oral liquid formulation as compared to placebo in the improvement of ASD core symptoms after 6 months of treatment in children aged from 2 to less than 7 years old with ASD	Childhood Autism Rating Scale, Second Edition (CARS2) total raw score. Main expression will be change from baseline to 6 month.

	Objectives	Endpoints
Secondary	To assess the effect of bumetanide on the other efficacy endpoints	
 - The change in SRS-2 total raw score from baseline to 6 month - CGI-I score at 6 month - The change in VABS II subscores from baseline to 6 month - The change in each individual CARS2 domain from baseline to 6 month
	To assess the safety of bumetanide	
 - Adverse events (AE), Paediatric Adverse Event Rating Scale (PAERS) - Clinical laboratory evaluation - Vital signs and clinical examination: weight (kg), height (m), Body Mass Index (BMI) (kg/m²), systolic blood pressure (mmHg), standing, sitting; Diastolic blood pressure (mmHg), standing, sitting, heart rate (bpm) - Electrocardiogram - Renal ultrasound - Assessment of suicidal ideation and suicidal behaviour using the Columbia Suicide Severity Rating Scale Children's version (C-SSRS-C)
	To confirm the acceptability and palatability of the oral liquid formulation	Acceptability and palatability questionnaire
	To describe the bumetanide effects on patients' quality of life	
 - Paediatric Quality of Life Inventory (PedsQL) expressed in term of change from baseline to month 6 - WHOQOL-Bref questionnaire summarized at each planned visit for each period using descriptive statistics
	To improve existing pharmacokinetic model of bumetanide in this population	PK points at W012 and W026
Exploratory	To describe the Bumetanide effect on utility index scores	Utility index score on the EQ-5D-3L

Refer to sections 6.1 and/or 7.1 for further details.

4.2. Experimental design

4.2.1. Study plan

This study is divided into the following periods:

1. A run-in period up to 4 weeks between selection (ASSE) and inclusion (week 0) visits:
This period is without Investigational Medicinal Product (IMP) treatment to evaluate eligibility. Stable psychosocial intervention is maintained if any.
This period allows investigators to perform ECG, renal ultrasound, laboratory examinations, and to complete, if needed, the wash-out period of forbidden treatments before inclusion.

2. Double-blind treatment period of 6 months between inclusion (week 0) and month 6 (week 26):

At inclusion patients will be randomised to one of the two parallel groups: bumetanide 0.5mg BID or placebo BID. The treatment (bumetanide or placebo) will be assigned at inclusion by a balanced randomisation (ratio 1:1).

- Patients randomised in the bumetanide arm will receive bumetanide up to 0.5mg BID. Bumetanide doses will be adapted on body-weight:
 - o If their weight is < 25kg, they will receive bumetanide 0.02 mg/kg BID (oral solution 0.5 mg/mL) corresponding to a volume of solution of 0.04 ml/kg BID from inclusion to month 6
 - o If their weight is \geq 25kg, they will receive bumetanide 0.5mg BID (1mL oral solution BID) from inclusion to month 6
- Patients randomised in the placebo arm will receive placebo BID
The volume of the oral solution will be calculated on body-weight:
 - o If their weight is < 25kg, they will receive placebo BID (corresponding to a volume of placebo solution of 0.04 ml/kg BID) from inclusion to month 6
 - o If their weight is \geq 25kg, they will receive placebo BID (1mL placebo BID oral solution) from inclusion to month 6

Stable psychosocial intervention is maintained if any.

3. Open label active treatment period of 6 months between month 6 (week 26) and month 12 (week 52):

- Patients randomised in the bumetanide arm during the double blind period will continue to be treated by bumetanide up to 0.5mg BID during the whole open label period. Bumetanide doses will be adapted on a body-weight as in the double blind period.
- Patients randomised in the placebo arm during the double blind period will receive bumetanide up to 0.5mg BID during the whole open label period. Bumetanide doses will be adapted on a body-weight as in the double blind period.

4. A follow-up visit (Wend), 6 weeks after treatment discontinuation:

This period is without any IMP and it will be completed at the end of the study or in case of premature discontinuation from the study at any moment.

The study plan is shown in [Figure \(4.2.1\) 1](#).

In case of non-inclusion of a participant, it is the investigator's responsibility to ensure, in accordance with the local standards of care and medical practices that:

- The reason of non-inclusion is explained to the participant and to his/her parents/legal representative,
- Any event associated with any procedure/condition required by the study protocol (e.g. an event occurring following the discontinuation of a forbidden treatment) is collected,
- Adequate medical care is proposed to the participant.

[figure not shown]
A non-inclusion visit is not mandatorily carried out, provided these requirements are met and documented in the medical file of the participant.

The following variation can be accepted:

- Variation of maximum \pm 1 day between visits is allowed for W000+Day10, W000+Day17 and W004 visits
- Variation of maximum \pm 2 days between visits is allowed for , W008, W012, W016, W020 and W026 visits

- Variation of maximum ± 1 day between visits is allowed for W026+Day10, W026+Day17 and W030 visits
- Variation of maximum ± 2 days between visits is allowed for W034, W038, W042, W046 and W052 visits

Figure (4.2.1) 1 – Study plan

The study start is defined as the date of the first visit of the first participant (selection visit - ASSE).

A 6-month extension period in open-label is proposed in some countries where it is not possible to provide the treatment at the end of the main periods *via* a Named Patient Basis (NPB) access or a Post-Access Study Program.

Therefore, the End of Trial is defined as the date of the last follow-up visit of the last participant (including a phone contact) in the open label active treatment period or in the extension period whichever occurs the latest, or the date of the last contact attempt if the last participant is declared lost to follow-up.

4.2.2. Investigation schedule

Table (4.2.2) 1 describes the measurement of efficacy and safety assessed during the study.

Table (4.2.2) 1 - Investigation schedule

	Selection	Inclusion	Double-blind 26 week treatment period									Visits to complete in case of IMP discontinuation during the double blind period BUT not withdrawal from the study		
			ASSE	W000	W000 48/72h	W000 Day 10	W000 Day 17	W004	W008	W012	W016	W020	W026	W012
Informed consents/assents	X ⁽¹⁾													
Demography	X													
IQ test ⁽⁴⁾	X													
DSM-5	X													
ADOS-2 ⁽²⁾	X													
ADI-R ⁽⁴⁾	X													
Selection / Non selection criteria	X													
Inclusion / Non-inclusion criteria		X												
Autism diagnostic history	X													
Medical / surgical history	X													
Previous treatments ⁽⁵⁾	X													
Concomitant treatments ⁽⁵⁾	X	X	X	X	X	X	X	X	X	X	X	X	X	X
IRS														
Patient number	X													
Randomisation		X												
IMP allocation		X												
IMP dispensation		X					X	X	X	X	X	X ⁽⁶⁾		
Oral solution volume adaptation to patient weight if needed		X					X	X	X	X	X	X		
Compliance IMP							X	X	X	X	X	X		

(1) To obtain at the latest at ASSE but before any procedure related to the study

(2) Only to be performed if retrospective exam is not available in the 12 months prior to ASSE

(3) Should not be performed if an ADOS-2 evaluation has been done within the 12 months prior to ASSE and is documented in the site

(4) Only to be performed if retrospective ADI-R is not available after the 4 y.o. of the patient

(5) Including non-pharmacological therapies (psychotherapy, social skills training, behavioural interventions, etc)

(6) First IMP dispensation of the open label 26 week active treatment period

Table (4.2.2) 1 – Investigation schedule (continued)

	Selection	Inclusion	Double-blind 26 week treatment period									Visits to complete in case of IMP discontinuation during the double blind period BUT not withdrawal from the study		
			ASSE	W000	W000 48/72h	W000 Day 10	W000 Day 17 D017	W004	W008	W012	W016	W020	W026	W012
Efficacy measurements														
CARS2-HF/ CARS2-ST/ CARS2-QPC		X				X		X			X		X	X
CGI	X ⁽¹⁾	X ⁽¹⁾			X ⁽²⁾	X ⁽²⁾	X ⁽²⁾	X	X ⁽²⁾	X ⁽²⁾	X		X	X
SRS-2		X				X		X			X		X	X
VABS II		X									X			
Safety measurements														
Suicidality (C-SSRS-C)		X						X			X			
Adverse events		X	X	X	X	X	X	X	X	X	X	X	X	X
PAERS scale		X			X	X	X	X	X	X	X		X	X
Laboratory tests (blood and urine)	X							X			X			
Blood electrolytes monitoring (K, Na) (performed locally except at ASSE)	X		X	X	X	X	X ⁽³⁾	X	X ⁽³⁾	X ⁽³⁾	X			
ECG	X ⁽⁶⁾					X ⁽³⁾	X ⁽³⁾	X ⁽³⁾					X ⁽³⁾	
Renal ultrasound	X												X ⁽³⁾	
Sitting and standing blood pressure/Heart rate	X	X			X			X					X	
Body Weight and Height	X	X ⁽⁴⁾			X ⁽⁴⁾	X ⁽⁴⁾	X ⁽⁴⁾	X	X ⁽⁴⁾	X ⁽⁴⁾	X		X	
Pharmacokinetics (blood samples)								X					X	
Other measurements														
PedsQL		X				X		X					X	
WHOQOL-Bref		X				X	X	X					X	
EQ5D-3L		X						X					X	
Acceptability Questionnaire													X	

(1) CGI-S only

(2) CGI-4 only

(3) Prescribed based on the clinical opinion of nephrologist or investigator

(4) Only body weight

(5) Results of the exam should be available at this visit prescription to be done at the previous visit

(6) ECG Triplicate only at ASSE

Table (4.2.2) 1 – Investigation schedule (continued)

	Open label 26 week active treatment period									FU	WD Withdrawal visit to be undergone in case of IMP definitive discontinuation or in case of total withdrawal from the study whatever the period
	W026 48/72h	W026 Day 10	W026 Day 17 (D199)	W030	W034	W038	W042	W046	W052		
Concomitant treatments ⁽¹⁾	X	X	X	X	X	X	X	X	X	X	X
IRS				X	X	X	X	X			
IMP allocation				X	X	X	X	X			
IMP definitive discontinuation											X
IMP dispensation				X	X	X	X	X			
Oral solution volume adaptation to patient weight				X	X	X	X	X			
Compliance IMP				X	X	X	X	X	X		X
Efficacy measurements											
CARS2-HF/ CARS2-ST ³ /CARS2-QPC						X			X	X	X ^{(6) (7)}
CGI						X ⁽⁶⁾			X	X	X ⁽⁶⁾
SRS-2						X			X	X	X ^{(6) (7)}
VABS II									X		X ^{(6) (7)}
Safety measurements											
Suicidality (C-SSRS-C)						X			X		X
Adverse events	X	X	X	X	X	X	X	X	X	X	X
PAERS scale			X	X	X	X	X	X	X		X
Laboratory tests (blood and urine)						X			X		X
Blood electrolytes monitoring (K, Na) (performed locally except at WD)	X	X	X	X	X ⁽⁴⁾	X	X ⁽⁴⁾	X ⁽⁴⁾	X		X
ECG				X ⁽⁵⁾	X ⁽⁵⁾	X ⁽⁵⁾			X ⁽⁵⁾		X
Renal ultrasound									X ⁽⁵⁾		X
Sitting and standing blood pressure/ Heart rate			X			X			X		X
Body Weight and Height			X ⁽⁶⁾	X ⁽⁶⁾	X ⁽⁶⁾	X	X ⁽⁶⁾	X ⁽⁶⁾	X		X
Other measurements											
PedsQL				X		X			X		X ^{(6) (7)}
WHOQOL-Bref				X	X	X			X		X ^{(6) (7)}
EQ5D-3L						X			X		X ^{(6) (7)}
Acceptability Questionnaire									X		X ⁽⁷⁾

(1) Including non-pharmacological therapies (psychotherapy, social skills training, behavioural interventions, etc)

(2) Prescribed based on the clinical opinion of nephrologist or investigator

(3) Only body weight

(4) Only to be undergone after the last IMP intake by patients discontinuing prematurely from the study after W000 Day10

(5) Results of the exam should be available at this visit, prescription to be done at the previous visit

(6) CGI-I only

(7) Should not be done in case of study discontinuation for consent withdrawal

For further practical details, methods of measurement are provided in sections 7, 8 and 9.

For organisational reasons ASSE, W000, W012, W026, W038 and W052 visits can be split in several days, in order to be able to complete all the study evaluations.

The following recommendations should be followed:

For ASSE:

- ECG, renal ultrasound and laboratory tests could be performed after ASSE visit date but always during the run in period and results must be available for the inclusion visit

For W000, W012, W026, W038, W052:

- CARS2 and CGI study assessments planned at the corresponding visit should be performed on the same day
- efficacy evaluations should be always performed prior to any safety procedure in case both efficacy evaluations and safety procedures have been planned to be performed on the same day,
- parents questionnaires (CARS QPC, SRS2 and quality of life questionnaires) and Vineland scale could be completed on site within 3 days prior to the day of the visit,
- safety evaluations could be done within 7 days prior to the visit date.

Furthermore, taking into account local regulation, it is not compulsory for the patient to attend the visits W000+48h/72h, W000+Day 10, W000+Day17, W026+48h/72h, W026+Day 10 and W026+Day17 on site.

In such a case the following recommendations should be followed:

- The planned blood sampling for electrolytes (Na and K) at these visits will be performed locally.
- A phone contact must be established by the investigator with the patient (when possible) and the parent(s)/ legally representative or caregiver (when applicable) in order to collect any adverse event at these visits.
- vital signs will be collected at home by a study nurse when required.

Special conduct in the case of definitive discontinuation of IMP during the double blind period:

1. Patient will complete the study evaluations planned at WD visit.
2. If IMP definitive discontinuation occurs prior to W012:
 - a. patient will attend W012 visit (if there is at least 2 months between WD and W012) and will be invited to complete CARS2, SRS-2, CGI and AE assessment at W012 as planned in the investigation schedule (Table (4.2.2) 1).
 - b. patient will attend then W026 visit and will be invited then to complete CARS2, SRS-2, CGI and AE assessment at W026 visit as planned in the investigation schedule (Table (4.2.2) 1).
3. If IMP definitive discontinuation occurs between W012 and W026:
 - a. patient will attend W026 (if there is at least 2 months between WD and W026) and will be invited to complete CARS2, SRS-2, CGI and AE assessment at W026 as planned in the investigation schedule (Table (4.2.2) 1).

In such a case, CARS2, SRS-2, CGI evaluations and AE assessments at W012 and W026 will be completed ONLY if the patient who has definitively discontinued the IMP during the

double blind period, does not require an important modification on his/her current background medical care (see section 5.6.1.).

The conduct in the case of definitive discontinuation of IMP during the double blind period is summarized in the Table (4.2.2) 2.

Table (4.2.2) 2 - Conduct in case of definitive discontinuation of IMP during the double blind period without study withdrawal

Visit (when IMP is definitely discontinued)	WD (to be performed)	W012 (to be performed)	W026 (to be performed)	Wend (to be performed)
D017	x	x	x	NA
W004	x	x	x	NA
W008	x	NA	x	NA
W012	x	NA	x	NA
W016	x	NA	x	NA
W020	x	NA	NA	X
W026	x	NA	NA	X

NA: Not applicable

The maximum total volume of blood collected per participant during the study will be 34 mL. See Table (4.2.2) 3

Table (4.2.2) 3 – Volume (mL) of blood collected per participant during the study

	ASSE	W000 + 48/72h	W000 + Day 10	W000 + Day 17	W004	W012	W026
Haematology	1					1	1
Biochemistry	4					2.5	2.5
Serology							
Pharmacokinetic						1	1
Na/K monitoring	1	1	1	1	1	1	1
TOTAL volume (mL) per visit	6	1	1	1	1	5.5	5.5
	W026 + 48/72h	W026 + Day 10	W026 + Day 17	W030	W038	W052	
Biochemistry					2.5	2.5	
Haematology					1	1	
Na/K monitoring	1	1	1	1	1	1	
TOTAL volume (mL) per visit	1	1	1	1	4.5	4.5	
TOTAL volume (mL) per participant	34						

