5.6. Participant withdrawal

5.6.1. Withdrawal criteria

Premature discontinuation of IMP during the double blind treatment period (W000-W026) does not mean that the participant prematurely stops the participation in the study.

In the case of premature discontinuation of IMP during the double blind period and, if the patient does not require an important modification on his/her current background medical care, he/she will be invited to complete CARS2, SRS-2, CGI evaluations and AE assessment for W012 (if discontinuation occurs prior to W012) and W026 visit as planned in the investigation schedule (Section 4.2.2).

Important modification of current medical care is defined as follows:

- *Newly initiated formal behavioural, cognitive or cognitive-behavioural therapy*
- *Increase/decrease weekly prescribed hours >25% of behavioural, cognitive or cognitive-behavioural therapy*
- *Newly initiated or recently changed pharmacotherapy:*
 - o *Introduction of a psychotropic medication (considered as forbidden in the study, section 6.3)*
 - o *Introduction or dose increase of an antipsychotic*
 - o *Introduction or dose increase of ADHD treatment*

The following criteria will lead to a premature discontinuation of IMP:

- Serum potassium levels < 3mEq/L
- Any suicide attempt, whatever its severity
- High suicidal risk, according to investigator's judgment or with a suicidal ideation of 4 or 5 on C-SSRS-C
- Nephrocalcinosis observed at the renal ultrasound
- Occurrence of seizure(s)
 - o in a patient without any medical history of seizure.
 - o or in a patient with a medical history of seizure if this require any modification of the on-going anti-epileptic treatment.
- Any symptoms or signs of potential renal function failure.
- eGFR $\leq 80\text{mL}/\text{min}/1.73\text{m}^2$ (estimated glomerular filtration rate, Schwartz formula 2009).
- Clinically relevant nephropathy according to investigator's clinical judgment (based on broader sources including risk factors, medical history, clinical examination and biological parameters).
- Clinically relevant hypercalciuria.

In case of abnormal urinary calcium/creatinine ratio that may be the expression of a clinically relevant hypercalciuria, a retest should be performed as soon as possible. Based on these results, the investigator should have a discussion with the local paediatric nephrologist in order to assess whether it corresponds to the presence of a clinically

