relevant hypercalciuria according to their clinical judgment (based on broader sources including risk factors, medical history, clinical examination and other biological parameters).

Additional urinary retest(s) and other appropriate exams should be performed if they judge them as relevant for the patient's safety.

- Absence of 2 consecutive planned electrolytes monitoring analysis.
- Absence of 2 consecutive planned urinary monitoring analysis.
- Occurrence of QT prolongation ($QTc_F \geq 480\text{ms}$), torsade de pointe and ventricular arrhythmia. Even if a 12-lead ECG reading and interpretation will be centralised, a local assessment of ECG exams is necessary for detection of medical urgencies and must be enclosed in the source data. Central reading reports for ECG overrule local reading for inclusion/exclusion/withdrawal criteria.
- Occurrence of a new psychiatric or other medical conditions leading to necessary administration of forbidden concomitant medication or likely to interfere with the conduct of the study.
- Any event or circumstances related or unrelated to the treatment justifying the discontinuation of treatment in the investigator's opinion (including treatment failure i.e. lack of efficacy).
- Major deviation to protocol if it interferes with the study evaluations and/or if it jeopardises participant's safety, e.g. any medical event requiring administration of an unauthorised concomitant treatment (see section 6.3).

Other criteria for premature discontinuation of IMP and for premature withdrawal from the study:

- Lost-to-follow up.
- Any non-medical circumstances leading to patient withdrawal (e.g. assent/consent withdrawal).

Information to be collected during the last visit of these participants is given in Section 5.6.2. These follow-up modalities are used to ensure the efficacy and safety evaluation of all participants who received the IMP.

Special conduct in case of gastrointestinal symptoms and weight loss

If the patient experiences digestive symptoms (≥ 3 liquid stools per day and/or ≥ 3 vomits per day) or digestive symptoms with a weight loss greater than 5%, the study treatment should be temporarily interrupted. Such an interruption will last 48h/72hours.

In such a case a monitoring of K^+ , Na^+ must be done locally prior to study treatment re-introduction. Further electrolytes follow up will be locally done according to the clinical opinion of the medical doctor.

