1.2.1. Study plan

The study is divided into the following periods:

- A run-in period without treatment up to 4 weeks (from ASSE to W0) to allow investigators to perform ECG, renal ultrasound, laboratory examinations and to respect the wash-out period of any unauthorised treatment before inclusion.
- A double-blind period of 6 months (from W000 to W026): at W000, patients are randomised (1:1) in double-blind conditions to one of the two treatment groups: bumetanide or placebo.
- An open-label period of 6 months (from W026 to W052):
 - Patients randomised in the S95008 arm during the double-blind period will continue to be treated by S95008 during the whole open-label period.
 - Patients randomised in the placebo arm during the double-blind period will receive bumetanide during the whole open-label period.
- A follow-up period of 6 weeks after treatment discontinuation (from W052 to WEND). A WEND visit should be planned 6 weeks after Investigational Medicinal Product (IMP) stop (W052 or premature withdrawal).
- A 6-month optional extension period with Bumetanide is proposed in some countries where it is not possible to supply Bumetanide (study formulation) at the end of the follow up period via a Named Patient Basis (NPB) access or a Post-Access Study Program. This extension is optional and proposed to the patients based on the investigator's clinical judgement (clinical benefit observed during the main study without no major safety concern).

IMPs are supplied as two oral administrations per day with 1 mL graduated pipette upon waking in the morning and in the afternoon, 3 hours before going to bed at the latest.

[figure not shown]
The volume of the oral solution will be adapted according to a body-weight basis for patients with a weight lower than 25 kg.

The appearance and taste of the solution are the same for all IMPs throughout the study. The first IMP intake takes place on the day of the inclusion visit in the afternoon.

An adaptation of the oral solution volume according to the weight of the patients will be performed during the study at visits W012, W026 and W038.

The study plan is shown in [Figure \(1.2.1\) 1](#).

Figure (1.2.1) 1 - Study plan

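### After a definitive drug stop, the scheduled W012/W026 adverse event assessment depends on unchanged background care, a condition that fits only the efficacy scales, and Table (4.2.2) 2 has no branch for a child whose care changes

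*Protocol*

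**What the plan says.** Protocol 4.2.2 sets out what happens when a child stops study drug for good during the double-blind period. The child has the withdrawal assessments (WD) and then returns for W012 and/or W026, depending on when the stop occurred. For an early stop, "patient will attend then W026 visit and will be invited then to complete CARS2, SRS-2, CGI and AE assessment at W026 visit". The section then adds that "CARS2, SRS-2, CGI evaluations and AE assessments at W012 and W026 will be completed ONLY if the patient who has definitively discontinued the IMP" needs no important modification of background care.

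Section 5.6.1 carries the same condition: if care is not importantly modified, "he/she will be invited to complete CARS2, SRS-2, CGI evaluations and AE assessment for W012 (if discontinuation occurs prior to W012) and W026 visit". It defines an important modification as a new behavioural or cognitive therapy, a change of more than 25% in weekly therapy hours, or certain drug changes. The drug changes are a forbidden psychotropic, or the start or increase of an antipsychotic or ADHD drug.

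Table (4.2.2) 2 summarises conduct by the visit at which drug is stopped. For stops at D017 to W016, W026 is to be performed and Wend is not applicable. For stops at W020 and W026, W026 is not applicable and Wend is marked. No row or note deals with changed care.

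On the follow-up visit, Protocol 4.2.1 describes "A follow-up visit (Wend), 6 weeks after treatment discontinuation" and adds that "it will be completed at the end of the study or in case of premature discontinuation from the study at any moment". SAP 1.2.1 says: "A WEND visit should be planned 6 weeks after Investigational Medicinal Product (IMP) stop (W052 or premature withdrawal".

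**The concern.** A new therapy or psychotropic drug can distort CARS2, SRS-2 and CGI, so withholding those ratings after a care change is defensible. It does not make an AE report uninterpretable in the same way, yet AE assessment sits in the same list under the same condition in both sections.

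The care change can also be part of why the drug was stopped. Section 5.6.1 requires a drug stop for "Occurrence of a new psychiatric or other medical conditions leading to necessary administration of forbidden concomitant medication", and counts "Introduction of a psychotropic medication (considered as forbidden in the study, section 6.3" among the important modifications. The condition can therefore remove scheduled AE assessment from children who have just developed a new problem.

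At stake is off-drug safety information up to W026. In SAP 3.6 and 3.6.1, serious emergent events and deaths are counted in period #1, which ends with the double-blind period including W26. AEs after the last intake are listed. Both outputs rely on someone asking about events after the drug has stopped.

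**Working it through.** The plan gives no figure on this point, and the sample size is not involved. The check has a textual part and a count of weeks.

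**Is there a branch for a child whose care changes?**

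1. Section 5.6.1 says that stopping the drug in the double-blind period is not in itself leaving the study. The reasons it gives for leaving are loss to follow-up and non-medical circumstances such as withdrawn consent. A care change is not among them.
2. Such a child therefore appears to fall under Table (4.2.2) 2, which covers children who stop drug but stay in the study. The table is keyed only to the visit of the stop. Wend is not applicable in 5 of its 7 rows, and in all 5 W026 is to be performed.
3. Section 4.2.2 has the child attend W026, but the only-if clause takes away all four assessments named for that visit.
4. Section 4.2.1 ties Wend to the end of the study or to leaving it. SAP 1.2.1 ties it to the drug stop. Neither says which applies here.

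**How long without a scheduled AE contact?**

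Inputs: nominal visit weeks from the schedule; WD taken at one week after the last dose, the latest time in 5.6.2; Wend, if held, six weeks after the stop.

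- Stop to W026 = 26 − week of stop
- WD to W026 = (26 − week of stop) − 1
- Wend to W026 = (26 − week of stop) − 6

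| Stop at | Stop to W026 (weeks) | WD to W026, no Wend | Wend to W026, if Wend is held |
|---|---|---|---|
| D017 | 26 − 17/7 = 23.6 | 22.6 | 17.6 |
| W004 | 26 − 4 = 22 | 21 | 16 |
| W008 | 26 − 8 = 18 | 17 | 12 |
| W012 | 26 − 12 = 14 | 13 | 8 |
| W016 | 26 − 16 = 10 | 9 | 4 |

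For a stop at W020, Wend is marked and falls at week 20 + 6 = 26, so no gap remains.

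The two right-hand columns assume that care changes before the next scheduled assessment. A child who stops at D017 or W004 and whose care changes only after W012 has already had the W012 assessment, which leaves 26 − 12 = 14 weeks to W026.

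**Scheduled AE contacts after WD**, for stops at D017, W004, W008, W012 and W016:

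- care unchanged: 2, 2, 1, 1, 1
- care changed before the next assessment, Wend taken as not applicable: 0 in each row
- care changed, Wend held at six weeks: 1 in each row

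**How many children?** The documents do not say. As an illustration only, the planned 15% withdrawal of 200 is 30 children. If all 30 stopped drug in these rows and 10% to 100% of them had a care change, 3 to 30 children would be affected. Both the share and the use of the withdrawal rate for drug stops are assumptions.

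**The case against.** The strongest reply is that the branch is implied. A child barred from all four assessments has no double-blind activity left and has in substance left the study, so 4.2.1 gives a Wend, where Table (4.2.2) 1 schedules AE collection. The study summary also describes follow-up of six weeks after drug discontinuation, and SAP 1.2.1 agrees. Table (4.2.2) 2 follows the same logic: wherever W026 is not applicable, Wend is marked.

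This is a sensible reading and may be what was meant. But no sentence equates changed care with leaving the study, and 5.6.1 points the other way. Even on this reading, 4 to 17.6 weeks after Wend have no scheduled AE contact.

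The second reply is that other routes remain, and this stands:

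- WD collects AEs, with PAERS, laboratory tests, ECG, renal ultrasound and C-SSRS-C.
- Section 8.9.1 keeps the reporting duty for children who stop drug but still participate, and sets no time limit for related serious events.
- Sections 8.7 and 8.9.2.5 require immediate notification, within 24 hours, of serious events and events of special interest.
- Section 8.9.2.2 provides follow-up of known events.
- The SAP treats the drug as short-acting, and its TEAE window closes two days after the last intake.

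A reader might infer that AE collection simply ends at WD for these children. Given these provisions, the documents do not support that. What the clause removes is a scheduled occasion to ask.

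**Conclusion.** The concern holds as a weakness in safety ascertainment and a gap in clarity. Two sections make a scheduled AE assessment depend on a condition suited only to efficacy ratings, and the conduct table does not cover the child affected.

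The unscheduled stretch before W026 is about 9 to 22.6 weeks from WD if Wend is taken as not applicable, or 4 to 17.6 weeks from Wend if it is held. These figures rest on nominal visit dates, WD one week after the last dose, and a care change before the next scheduled assessment.

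The outputs that may be affected are new serious events and deaths in period #1, and the listing of AEs after the last intake. The TEAE tables, related serious events and follow-up of known events are largely untouched. Efficacy analyses, estimand and sample size do not change.

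Two further inferences go beyond the text. One is that period #1 must under-count: the SAP does not fix the end of that period for a child who stops early and misses W026, so the effect is possible but not shown. The other is that a child without Wend has no start for the 30-day window for immediately notifiable events: 8.9.1 introduces that window as following the last study visit, which supplies one.

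**What to change.** - In 4.2.2 and in the matching condition in 5.6.1, limit the requirement of unchanged care to CARS2, SRS-2 and CGI. AE assessment at W012 and W026 is then done for every child still in the study, by phone if the family does not attend.
- Add a footnote to Table (4.2.2) 2: where W026 is not performed, Wend applies, or an AE phone contact about six weeks after the drug stop.

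The cost is wording in two sections and one table, plus at most one or two phone contacts per affected child: two for stops at D017 or W004, one otherwise. Section 4.2.2 already uses phone contact to collect AEs at the early visits that need not be on site. With the change, every row of the table has at least one scheduled AE contact after WD, whatever the child's care status.
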